## 6 ANALYSIS POPULATION

Membership of the analysis populations will be reviewed and agreed at a Data Review Meeting (DRM) before database lock.

### 6.1 OBSERVED CASES (OC) SET

The Observed Cases (OC) Set is defined as those subjects included in the study, who have received at least one dose of the study treatment. This set will use all data available at timepoints without any imputations for missing dichotomous values, and with Last Observation Carried Forward (LOCF) imputation (described in section 10.4) for missing continuous values.

The OC Set will be used for all safety and efficacy analyses.

## 6.2 NON-RESPONDER IMPUTATION (NRI) SET

The Non-responder Imputation (NRI) Set will consist of all patients in the OC Set with the following rules applied to the missing values:

- for dichotomous values, patient will be considered as non-responder
- for continuous values, LOCF imputation will be applied as described in section 10.4.

Efficacy analyses will be repeated for the NRI Set.

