9.1.1. Protocol deviations

Protocol deviations will be reviewed and classed as critical (immediate impact on patient safety or data integrity), major or minor during the data-review meeting. Major protocol deviations are defined as deviations liable to bias the evaluation of the main efficacy endpoint. The following deviations will be considered as major (non-exhaustive list):

- Non-compliance with the inclusion or exclusion criteria;
- Non-compliance with the study treatment;
- Intake of prohibited medication;
- Noncompliance with time window.

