9.1.2. Definition of study analysis sets

The following datasets will be defined and used for the analyses:

- The **Safety dataset (SAF population)** is defined as those subjects included in the study, who have received at least one dose of the study treatment.
- The **Full Analysis dataset (FAS population)** is defined as those subjects included in the study, who have received at least one dose of the study treatment, and who have at least one baseline data.
- The **Per Protocol dataset (PP population)** is defined as those subjects of the FAS population without any major protocol deviation.

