9.2. Efficacy Analysis

All efficacy analysis will be conducted on both FAS population and PP population except if otherwise specified.

Descriptive statistics will be presented by treatment arm and include:

- Quantitative variables: mean, standard deviation, minimum and maximum, 95% confidence intervals, median and quartiles will be presented when considered relevant. Number of filled and missing values will also be presented.
- Qualitative variables: count, percentage for each modality and 95% confidence intervals when relevant. Number of missing values will also be presented.

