### 1.2 CHANGES FROM PROTOCOL

- The echocardiography secondary endpoints will be included in a separate report.
- Sustained clinical remission and sustained endoscopic remission/improvement will be summarized as part of the secondary endpoints.
- Observed Cases (OC) Set and Non-responder Imputation (NRI) Set are defined for populations instead of the populations defined in the protocol.
- In the definition of corticosteroid-free clinical remission (Section 11.3.1.6), time interval is changed from 12 weeks to 90 days for consistency with other Abivax studies.
- In the definition of clinical response (Section 11.3.1.6), Modified Mayo Score is used instead of Total Mayo Score for consistency with other Abivax studies.
- All efficacy variables will be summarized based on the following subgroups:
  - Patients being in clinical response at BOLS and not being in clinical response at BOLS
  - Patients previously treated with biological drugs and naive from biological drugs.
- In the Synopsis and Section 2.4 of the protocol, M24 is missing from the list of timepoints for clinical remission, clinical response, endoscopic improvement, endoscopic remission and corticosteroid-free clinical remission inconsistently with further sections. This timepoint is included in the current SAP to ensure that these secondary endpoints are analysed for all required timepoints.

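### Apart from corticosteroid-free remission, no SAP analysis set or endpoint rule accounts for prohibited UC medication, so a patient in remission on such a drug is a responder in both the OC and NRI sets

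*SAP*

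**What the plan says.** **Protocol.** Section 9.1.1 states: "Major protocol deviations are defined as deviations liable to bias the evaluation of the main efficacy endpoint". Its list of examples includes "Intake of prohibited medication". Section 9.1.2 defines the PP population as "those subjects of the FAS population without any major protocol deviation", and section 9.2 plans both views: "All efficacy analysis will be conducted on both FAS population and PP population except if otherwise specified". The UC drugs prohibited in section 6.8.2 are anti-TNF agents, vedolizumab, JAK inhibitors, cyclosporine, tacrolimus, and topical corticosteroids and topical 5-ASA.

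**SAP.** Section 1.2 records the change without giving a reason: "Observed Cases (OC) Set and Non-responder Imputation (NRI) Set are defined for populations instead of the populations defined in the protocol". The OC Set (6.1) is every patient with at least one dose: "This set will use all data available at timepoints without any imputations for missing dichotomous values". The NRI Set (6.2) is the same patients, with one rule for missing binary outcomes: "for dichotomous values, patient will be considered as non-responder". Section 10.4 rules out any other imputation.

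The definitions in SAP 11.3.1.6 to 11.3.1.8 rest on Mayo sub-scores or score changes. The one exception is corticosteroid-free remission, which requires at least 90 days without corticosteroids and is defined among patients already in remission at the ABX464-102 baseline.

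**The concern.** The protocol treated use of a prohibited drug as something that could distort the efficacy result, and it planned an analysis without those patients. Under the SAP no analysis leaves them out. If such a patient remains in follow-up and has a qualifying score, nothing is missing, so NRI does not touch the value and the success is credited to ABX464.

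This study has no concurrent control and runs for 48 months, so the response rates are its efficacy message. Readers will take the NRI rate as the cautious one. On this point it is no more cautious than the OC rate.

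**Working it through.** **Step 1. Follow one patient through each planned analysis.** Suppose a patient starts an anti-TNF, stays in the study and meets the remission criteria at a scheduled timepoint.

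| Analysis | Treatment of this patient |
|---|---|
| Protocol FAS | responder |
| Protocol PP | excluded (major deviation) |
| SAP OC Set | responder |
| SAP NRI Set | responder (value is observed) |

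The Data Review Meeting in SAP section 6 cannot change this, because membership of both sets depends only on having taken one dose.

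**Step 2. Can such a patient stay in the study?** Protocol 7.2 does not name prohibited-drug intake as a reason for discontinuation, and withdrawal for treatment failure is optional. So yes, although an investigator may withdraw the patient.

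**Step 3. What happens to patients who are withdrawn first?** Protocol 5.2.6 gives them an End of Study visit four weeks after stopping, with no sigmoidoscopy listed. Their later binary outcomes are missing, and NRI already counts them as non-responders. The gap concerns only those who stay.

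**Step 4. Size.** The plan states no figure to reproduce; sample size is not applicable in both documents. The inputs come from Protocol 1.3: 22 enrolled (15 previously on ABX464, 7 on placebo), 16 with a month 12 endoscopy, and 12 of those 16 in remission. I assume that all 22 were dosed and that the interim remission count meets the SAP definition. The number k of those 12 remitters on a prohibited UC drug is not in the documents; 0 to 4 is assumed for illustration.

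One patient's weight under a non-response rule:
- total: 1/22 = 4.5 points
- previously ABX464: 1/15 = 6.7 points
- previously placebo: 1/7 = 14.3 points

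Month 12 remission, with NRI non-response = (12 − k)/22 and OC with PP-type exclusion = (12 − k)/(16 − k):

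| k (assumed) | NRI, counted as non-responders | OC, excluded as PP would |
|---|---|---|
| 0 | 12/22 = 54.5% | 12/16 = 75.0% |
| 1 | 11/22 = 50.0% | 11/15 = 73.3% |
| 2 | 10/22 = 45.5% | 10/14 = 71.4% |
| 3 | 9/22 = 40.9% | 9/13 = 69.2% |
| 4 | 8/22 = 36.4% | 8/12 = 66.7% |

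Under the SAP as written, the rates stay at 54.5% and 75.0% whatever k is. The exact 95% interval for 12/22 is 32.2% to 75.6%, so the shift for one patient is small beside the sampling uncertainty. The OC column uses patients with an endoscopy as denominator. The footnote to the Table 14.2.5.1 shell uses all patients in the column instead; on that basis excluding one remitter moves 12/22 = 54.5% to 11/21 = 52.4%.

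**Step 5. Would the outputs reveal it?** SAP section 14 lists no protocol-deviation table or listing. Listings 16.2.9.2 and 16.2.9.3 give each drug with its dates, and Listing 16.2.6.1 gives response status by visit. Neither flags prohibited use, and nothing links the two.

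**The case against.** Counting outcomes as observed, whatever else the patient takes, is a legitimate choice in a descriptive open-label extension whose primary endpoint is adverse events. The change of sets is declared, and no test depends on it. The documents report no patient kept in the study on a prohibited UC drug. An investigator can withdraw such a patient, and the withdrawal table shell (Table 14.1.2) has a category for major protocol violation. All of this stands. It limits the weight of the point but does not supply the missing rule.

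Four stronger readings are tempting, and the documents do not support them:

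- **That these patients are responders in every analysis.** Corticosteroid users fail corticosteroid-free remission, and patients withdrawn before other therapy are NRI non-responders through missing data.
- **That the SAP created the problem.** FAS would have counted the same patients as responders. The SAP removed the only analysis that excluded them.
- **That readers could not find them.** The medication and Mayo listings allow them to be traced by hand.
- **That 4.5 points per patient is the cost of losing PP.** That figure is the effect of a new non-response rule. PP excluded patients and did not count them as failures; for one month 12 remitter the OC rate moves by 75.0 − 73.3 = 1.7 points.

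Nor would PP clearly have removed a patient for newly started systemic corticosteroids, since Protocol 6.8.2 names only topical ones. A rule of permanent failure after any single prohibited intake would also be too blunt: a short topical 5-ASA course early on would then mean failure through month 48.

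**Conclusion.** The point holds in this limited form. For clinical remission, clinical response, and the endoscopic and sustained endpoints, neither set accounts for prohibited UC medication, and the one planned analysis that excluded such patients is gone. A patient who stays and qualifies on such a drug counts as a success in both sets.

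The size is conditional. Each affected patient is worth 4.5 points of the total NRI rate under a non-response rule, and more within the prior-treatment groups. The number affected is unknown and may be zero. Since efficacy is secondary and descriptive, this affects how the rates are read and not a formal conclusion. It is a worthwhile, inexpensive improvement.

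**What to change.** 1. In SAP 6.2, for the binary efficacy endpoints, also count as a non-responder in the NRI Set any patient who has started an anti-TNF, vedolizumab, a JAK inhibitor, cyclosporine or tacrolimus on or before the assessment. If the sponsor prefers to leave the NRI Set unchanged, pre-specify this as a supplementary NRI analysis.
2. Settle short topical courses and newly started systemic corticosteroids patient by patient at the Data Review Meeting, with reasons recorded before database lock. Alternatively, handle them in a sensitivity analysis that excludes major deviations.
3. Keep the OC Set as observed.
4. Report the number of affected patients at each timepoint, and add a listing of major protocol deviations.

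The coded medications and dates are already collected, so the cost is a little more programming and a possibly less favourable NRI rate. This is an analysis rule only and changes nothing in patient management.

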## 7 SAFETY MONITORING

An independent Data Safety Monitoring Board (DSMB), with expertise and experience in the pathology, and without direct involvement in the conduct of the trial, is set up specifically to guarantee effective protection of subjects, ensure the ethical conduct of the trial, benefit/risk ratio of the trial, and to ensure the independent review of the scientific results during the trial and at the end of the trial.

The DSMB meetings were held on a monthly basis until December 2019 and then quarterly from January 2020 onwards. The DSMB may recommend the early termination of the trial at any time.

In addition, DSMB reviews all potential causally related Serious Adverse Events within 7 days of the initial report.

The DSMB has only a consultative role; it will inform the sponsor who will decide whether the DSMB recommendation will be followed. A DSMB charter must be available upon submission of the trial (initial protocol) to the relevant competent authorities.

An Independent Cardiovascular Safety Committee (ICVSC), comprised of 3 cardiologists with experience from drug development, will be formed as detailed in the Charter. The ICVSC will be responsible for an on-going evaluation of cardiac adverse events of special interest (Cardiac AESIs), for treatment emergent echocardiographic findings, and for treatment emergent changes of cardiac safety biomarkers (as detailed above). The ICVSC will review cardiac adverse events on an on-going basis, meet regularly and provide recommendations to Sponsor and DSMB regarding study procedures and conduct.

## 8 INTERIM ANALYSES

An interim analysis was performed at M12 outside of Simbec-Orion.

The study analysis will be performed after database lock occurring following the completion of the last subject or its early discontinuation.

## 9 DATA

### 9.1 ECRF DATA

CRF data will be provided by Simbec-Orion data management to the statistics department as Statistical Analysis System (SAS) datasets in Simbec-Orion standard format which will be used for programming the outputs to be included in the Clinical Study Report (CSR). Populated datasets will be available when programming starts. These may contain dummy data if real data are not yet available.

### 9.2 EXTERNAL DATA

#### 9.2.1 Laboratory Data

For hematology and biochemistry local laboratory are used. All lab dosages are done locally.

The following clinical laboratory parameters are measured:

*Hematology:* Hemoglobin, Hematocrit, White Blood Cell (WBC), Neutrophils, Lymphocytes, Monocytes, Eosinophils, Basophils, Platelet count, ESR, Fibrinogen, Prothrombin time and/or INR.

*Biochemistry:* Sodium, Potassium, Chloride, Calcium, Phosphate, Glucose, Blood Urea Nitrogen (BUN) or urea, Creatinine, Aspartate Transaminase (AST), Alanine Transaminase (ALT), Glutamate Dehydrogenase (GLDH), Lipase, Alkaline phosphatase, gamma-Glutamyl Transferase (gGT), Total bilirubin, Total protein, Albumin, Lactate Dehydrogenase (LDH), C-reactive protein (CRP), Creatine Phosphokinase (CPK), High-sensitive Troponin T and/or I, N-terminal pro-brain natriuretic peptide (NT-proBNP), Amylase.

*Stools:* Faecal calprotectin.

### 9.3 OTHER NON-CRF DATA

Local Laboratory Reference ranges will be provided by the laboratory before site initiation and the required parameters will be transcribed onto the Data Management Laboratory Reference Range Form by the CRA. The CRA will provide reference ranges to the DM, who will use them to verify data on CRF.

### 9.4 RANDOMISATION LIST

Not applicable for this study.

### 9.5 PROGRAMMING AND DATA REVIEW

Programming of analysis datasets, tables, figures and listings will be ongoing during the data management of the study. Outputs for the DSMB are reviewed, but not fully QCd. Outputs may be reviewed by ABIVAX before Database Lock (DBL).

When the final data are considered clean, key listings (to be agreed) will be run and distributed to the study team for review. A data review meeting will be held to discuss the outcome of this review and the imputations for the primary endpoint. Once all data issues have been resolved and the analysis populations approved, the database will be locked. The final run of outputs and quality control (QC) will then take place.

## 10 STATISTICAL METHODS

### 10.1 GENERAL PRINCIPLES

All variables will be presented descriptively.

All statistical methods will be based on the International Conference on Harmonisation (ICH) E9 document “Statistical Principles for Clinical Trials”.

Data will be summarised by treatment group (50mg ABX464 (101 study) + 50mg ABX464 (102 extension) and Placebo (101 study) + 50mg ABX464 (102 extension)). A total column showing all patients will be included for baseline, safety and efficacy summaries. Where appropriate, data will also be summarised by visit with summaries for each visit attended as scheduled and an additional summary for final (last scheduled visit or early withdrawal). The format of the summaries is defined in the shells at the end of this document.

In safety tables of continuous variables, standard descriptive statistics (Sample number n, mean, Standard Deviation (SD), Standard Error of the Mean (SEM), median, minimum and maximum) will be presented. In summary tables of continuous variables, standard descriptive statistics (n, mean, 95% confidence interval [CI], SD, median, minimum and maximum and quartiles) will be presented. The minimum and maximum statistics will be presented in summary tables to the same number of significant figures as the original data. The mean, median, SD and SEM will be presented to one more significant than the original data.

- For numeric data which includes non-numeric values (e.g. lab results reported as < 10 or >100) the following principles will be applied when summarising the data:
  - Below Limit of Quantification (BLQ) will be replaced with a value that is ½ of the lower limit of quantification (LLQ)
  - Results reported as < x will be treated in the same way as BLQ with LLQ=x
  - Otherwise SD and CI will not be calculated
  - Whenever meaningful, minimum, median and maximum will be presented based on the reported data (e.g. minimum = <10, median = 20, maximum = >100)

In summary tables of categorical variables, the number of non-missing observations by category will be presented with percentages. The number of missing observations will also be presented when non-zero. Unless otherwise specified, the denominator for each percentage will be the number of non-missing observations within the column. All percentages will be presented to one decimal place.

If changes in severity for the same Treatment Emergent Adverse Event (TEAE) have been reported separately but with the same adverse event (AE) number, they will be collapsed to a single AE with maximum severity for the summary tables but listed as reported.

Classifications of medical history, concomitant medication and adverse events will be sorted alphabetically within the summary tables.

If any laboratory assessments are repeated at the same visit, the result from the repeat assessment will be used in summaries. Both values will be listed.

Data collected on the eCRF will be presented within data listings. The data listings will be sorted by treatment group, patient number and visit. Visits outside the visit windows will be identified within the listings.

The date format for all output presentations will be 'ddMMMyyyy'.

All statistical analysis will be performed using SAS ® Enterprise Guide V 8.3 or higher.

If any of the assumptions underlying the formal statistical methods proposed are violated during the analysis of the final data, alternative statistical methods will be used and any changes documented in the statistical methods section of the CSR, including the rationale for use.

## 10.2 STRATIFICATION AND COVARIATE ADJUSTMENT

No stratification or covariate adjustment will be used in this study.

## 10.3 INTERACTIONS

No interactions to be performed.

## 10.4 MISSING DATA

For missing continuous variables, Last Observation Carried Forward (LOCF) imputation method will be used for both the OC Set and the NRI Set. Missing dichotomous variables will not be imputed in the OC Set but will be imputed in the NRI Set as non-responder.

There will be no other imputation of missing data in this study.

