## 11.3 EFFICACY ANALYSES

All efficacy analysis will be conducted on both OC Set and NRI Set except if otherwise specified and will be summarized based on the following subgroups:

- Patients being in clinical response at BOLS and not being in clinical response at BOLS
- Patients previously treated with biological drugs and naive from biological drugs.

Descriptive statistics will be presented by treatment group and include:

- Quantitative variables: n, mean, SD, minimum and maximum, 95% CI, median and quartiles will be presented when considered relevant. Number of missing values will also be presented.
- Qualitative variables: count and percentage. Number of missing values will also be presented.

Listings showing patients efficacy derivations for Mayo Scores, time to UC worsening and SF-36 Questionnaire will be produced for the efficacy endpoints. All efficacy data will be listed.

If a scheduled endoscopic assessment is not performed, then results from the closest unscheduled assessment within 1 month should be used if available.

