|                               | SD        | xx.xx  | xx.xx  | xx.xx           |
|                               | Minimum   | xx.x   | xx.x   | xx.x            |
|                               | Maximum   | xx.x   | xx.x   | xx.x            |
|                               | Median    | xx.xx  | xx.xx  | xx.xx           |
|                               | Quartiles | xx.xx – xx.xx                                      | xx.xx – xx.xx                                  | xx.xx – xx.xx   |
| BOLS                          | n         | xx (xx.x %)  | xx (xx.x %)                                    | xx (xx.x %)     |
|                               | Missing   | xx (xx.x %)  | xx (xx.x %)                                    | xx (xx.x %)     |
|                               | Etc       |  |  |                 |
| Change from BIS to BOLS       | n         | xx (xx.x %)  | xx (xx.x %)                                    | xx (xx.x %)     |
|                               | Mean      | xx.xx  | xx.xx  | xx.xx           |
|                               | Etc       |  |  |                 |
| Visit                         | n         | xx (xx.x %)  | xx (xx.x %)                                    | xx (xx.x %)     |
|                               | Missing   | xx (xx.x %)  | xx (xx.x %)                                    | xx (xx.x %)     |
|                               | Etc       |  |  |                 |
| Change from BIS to Visit      | n         | xx (xx.x %)  | xx (xx.x %)                                    | xx (xx.x %)     |
|                               | Mean      | xx.xx  | xx.xx  | xx.xx           |
|                               | Etc       |  |  |                 |

Version Date 20 MAY 2021

Template STATt004

Page 38 of 97

|                           |      |             |             |             |
|---------------------------|------|-------------|-------------|-------------|
| Change from BOLS to Visit | n    | xx (xx.x %) | xx (xx.x %) | xx (xx.x %) |
|                           | Mean | xx.xx       | xx.xx       | xx.xx       |
|                           | Etc  |             |             |             |

Etc

Partial Mayo Score (pMS)

Etc

Modified Mayo Score (MMS)\*

Etc

Partial Modified Mayo Score (pMMS)

Etc

---

\*Total Mayo Score and Modified Mayo Score are only collected at visits where an endoscopy is carried out.

The denominator for each percentage is the number of patients within the column.

BIS: Day 0 of ABX464-101 study

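### LOCF in both analysis sets makes the paired continuous efficacy tables duplicates with no observed-data summary, and whole-column denominators force equal OC and NRI success percentages

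*SAP*

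**What the plan says.** **Continuous data.** SAP 6.1 defines the OC Set as all treated subjects, "with Last Observation Carried Forward (LOCF) imputation (described in section 10.4) for missing continuous values". SAP 6.2 takes all OC patients into the NRI Set and says "for continuous values, LOCF imputation will be applied as described in section 10.4". SAP 10.4 repeats the rule: "For missing continuous variables, Last Observation Carried Forward (LOCF) imputation method will be used for both the OC Set and the NRI Set". It allows no other imputation. The sets differ only for missing dichotomous values, which stay missing in OC and become non-response in NRI.

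SAP 14.1 lists the continuous efficacy tables once per set: 14.2.1.1/2 (Mayo scores), 14.2.1.3/4 (Mayo components), 14.2.3.1/2 (calprotectin, CRP, ESR) and 14.2.4.1/2 (SF-36).

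**Text that points towards observed data.** SAP 10.1 says "data will also be summarised by visit with summaries for each visit attended as scheduled". A footnote to the Table 14.2.1.1 shell says "Total Mayo Score and Modified Mayo Score are only collected at visits where an endoscopy is carried out". SAP 11.3 substitutes the nearest unscheduled endoscopy within one month when a scheduled one was not done.

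**Denominators.** SAP 10.1 makes non-missing observations the default and allows exceptions. The shells for 14.2.5.1/2 and 14.2.6.1/2 take the exception and divide by all patients in the column. The shells for the shift tables 14.2.5.3/4 keep the default. SAP 11.3.1.6 restricts corticosteroid-free remission to patients already in remission at the open-label baseline (BOLS).

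**The concern.** An observed-case analysis and an imputed analysis are normally paired so that a reader can see how far the result depends on the imputation. Here the continuous pair cannot show that, because both members are imputed in the same way. The binary pair cannot show it in the Yes percentage, because the OC denominator already treats missing patients as if they had been counted and had failed.

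This matters because the cohort is 22 patients followed for 48 months, so missing values grow at the visits of most interest. Carried-forward values count as full observations and tighten the printed intervals. The SAP also does not limit LOCF to visits where the assessment was scheduled, and does not say whether a baseline value may be carried. Two programmers could therefore fill the endoscopy-based scores differently.

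**Working it through.** **1. Are the continuous tables duplicates?** Same patients (SAP 6.2) plus the same rule (SAP 6.1, 6.2, 10.4) give the same analysis values, hence the same n, mean, CI, SD, median and quartiles. Subgroup membership is one flag per patient (Listing 16.2.3), so the subgroup pages match too. A simulation of the two rules on 22 patients, assuming 25% of values missing after the first visit, gave identical summaries in 500 of 500 datasets.

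**2. How much is carried forward at Month 12?** Inputs from Protocol 1.3: 22 enrolled, 3 excluded from the Month 12 set, 16 with a Month 12 endoscopy. Check: 22 − 3 = 19, as the protocol states.
- Measures taken at each visit: 3/22 = 13.6% carried.
- Total and Modified Mayo Scores: up to 6/22 = 27.3% carried, if a visit without endoscopy counts as missing. The SAP 11.3 one-month rule lowers this where it supplies a value.

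**3. Effect on the printed 95% CI.** At equal SD, the ratio of the LOCF width to the observed width is [t(0.975, 21)/√22] / [t(0.975, n−1)/√n].

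| Observed n of 22 | Ratio | Basis |
|---|---|---|
| 19 | 0.920 | Month 12 visit attended |
| 16 | 0.832 | Month 12 endoscopy done |
| 14 | 0.768 | assumption, late visits |
| 12 | 0.698 | assumption, late visits |

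The figure of 14 is borrowed from Protocol 1.2.5 (patients treated for more than 3 years at 30 November 2021). It is not a Month 48 count. With 14 observed, 8/22 = 36.4% of values would be carried. For 12 to 16 observed, the ratio runs from 0.70 to 0.83.

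**4. Equal Yes percentages.** Let N be the column total, o the patients with a result and y the successes. With a whole-column denominator, OC Yes = y/N. NRI moves the N − o missing patients to No, so NRI Yes is also y/N. Illustration with the interim counts N = 22, o = 16, y = 12:
- OC: Yes 12/22 = 54.5%, No 4/22 = 18.2%, Missing 6/22 = 27.3%.
- NRI: Yes 12/22 = 54.5%, No 10/22 = 45.5%.
- OC shift Table 14.2.5.3: Yes 12/16 = 75.0% (exact 95% CI 47.6 to 92.7).

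The two OC figures for one visit differ by 75.0 − 54.5 = 20.5 points. The observed rate can be recovered from the Missing row: 12/(22 − 6) = 75.0%.

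**5. Corticosteroid-free remission.** A patient not in remission at BOLS cannot meet the definition in SAP 11.3.1.6. The footnote to Table 14.2.5.1 nevertheless puts that patient in the denominator, so the printed rate cannot exceed the share in remission at BOLS. The table title names three endpoints and the shell has three blocks, two of them headed Clinical Response.

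**The case against.** The study is open-label and descriptive, its primary endpoint is a count of adverse events, and no decision rests on the width of an efficacy interval. LOCF in the OC Set is stated openly. Listings 16.2.6.1, 16.2.6.3 and 16.2.6.4 keep the raw efficacy values, and each proportion shell prints its denominator and a Missing row. Simply dropping the second set of continuous tables would remove the duplication. All of this stands, and it limits the severity. It does not supply an observed-data summary, and dropping the duplicates would leave only the imputed version.

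Several stronger readings are tempting, but the documents do not support them:
- *The Missing rows contradict LOCF.* SAP 11.3 promises "Number of missing values will also be presented" and Protocol 9.2 "Number of filled and missing values will also be presented". These counts can describe values before imputation, or patients with no earlier value to carry, so they can coexist with LOCF.
- *The patient who left at Month 1 for lack of efficacy will print as zero change in Total Mayo Score.* That needs no as-needed endoscopy, baseline carried forward, and LOCF continued after withdrawal. The SAP states neither of the last two. Protocol 7.2 requires endoscopic confirmation of worsening; if that criterion was applied to this withdrawal, a later score would exist.
- *Laboratory and vital-sign means will be imputed.* SAP 10.4 is not limited to efficacy, and SAP 6.1 says "The OC Set will be used for all safety and efficacy analyses". But the by-visit rule in SAP 10.1 points the other way, and SAP 11.6.2 has its own laboratory rules and does not mention LOCF. This is a query, not a demonstrated error.
- *The sustained-endpoint tables 14.2.7.1/2 have no denominator.* They have one: the Table 14.2.6.1 layout applies to them and gives the column total.
- *Corticosteroid-free remission was left out of the shell.* A mislabelled block is more likely, since the endpoint appears in the title, in SAP 11.3.1.6 and in Listing 16.2.6.1.

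**Conclusion.** The point holds. That the four continuous pairs duplicate each other, and that the OC and NRI Yes percentages are equal, follows from the SAP text and footnotes without any assumption about the missing continuous values.

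The sizes are conditional. The CI ratios of 0.92 and 0.83 assume equal SD, and the 0.83 moves towards 0.92 where the one-month endoscopy rule supplies a value. Late-visit ratios rest on an assumed number observed. The contrast of 54.5% with 75.0% is an illustration: it assumes that the interim analysis, which was done outside the CRO, used the SAP remission definition, and that sub-scores are not carried forward before remission is derived. Endoscopy was not mandatory at Month 12 (Protocol 5.2.3), so the gap is likely larger there than at Months 24 to 48.

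This should be fixed before lock. It does not threaten the study's primary conclusion: treatment-emergent adverse event counts are unaffected.

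**What to change.** - **SAP 6.1 and 10.4:** use observed values only in the OC Set. Keep LOCF, if wanted, only in the second set and only at visits where the assessment is scheduled. State whether a baseline value may be carried.
- **OC Tables 14.2.5.1 and 14.2.6.1:** divide by patients with a result at the visit, which is the SAP 10.1 default. Keep the column total in the NRI tables 14.2.5.2 and 14.2.6.2.
- **Corticosteroid-free remission:** relabel its block in the 14.2.5.1 shell and use patients in clinical remission at BOLS as the denominator.
- **Safety:** add a sentence to SAP 10.4 confirming that it does not apply to safety variables.

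The cost is wording in the SAP and shells before database lock, with no new data. The downside is smaller n and wider intervals at late visits. SAP 10.1 already plans an extra summary at the last scheduled visit or early withdrawal, so early leavers would still be represented.
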